8.5. Adverse Events, Serious Adverse Events, and Other Safety Reporting

The definitions of AEs and SAEs can be found in [Appendix 4](#).

Adverse events will be reported by the participant (or, when appropriate, by a caregiver, surrogate, or the participant's legally authorized representative).

The investigator and any qualified designees are responsible for detecting, documenting, and recording events that meet the definition of an AE or SAE and remain responsible for following up all AEs (see [Appendix 4](#)).

The method of recording, evaluating, and assessing causality of AEs and SAEs and the procedures for completing and transmitting SAE reports are provided in [Appendix 4](#).

8.5.1. Time Period and Frequency for Collecting Adverse Event and Serious Adverse Events Information

All AEs and SAEs will be collected from the start of intervention until the follow-up visit at the time points specified in the SoA ([Section 1.3](#)).

Note: All SAEs that occur after the consent form is signed but before study intervention/treatment must be reported by the investigator if they cause the participant to be excluded from the trial, or are the result of a protocol-specified intervention, including but not limited to washout or discontinuation of usual therapy, diet, placebo treatment, or a procedure.

Medical occurrences that begin before the start of study intervention but after obtaining informed consent will be recorded as Medical History/Current Medical Conditions, not as AEs.

All SAEs will be recorded and reported to the sponsor or designee immediately and within 24 hours of first knowledge of the event by study personnel, as indicated in [Appendix 4](#). The investigator will submit any updated SAE data to the sponsor within 24 hours of it being available.

Investigators are not obligated to actively seek information on AEs or SAEs after conclusion of the study participation. However, if the investigator learns of any SAE, including a death, at any time after a participant has been discharged from the study, and he/she considers the event to be reasonably related to the study intervention or study participation, the investigator should promptly notify the sponsor.

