1.3. Schedule of Assessments

Table 3: Schedule of Assessments

Procedure	Screening		Baseline / Randomization	Double-blind Treatment Period (Treatment Period 1)		Washout Period	Double-blind Crossover Treatment Period (Treatment Period 2) (First Dose Taken Day 21 to 24)		SFU or ED	Notes
Visit Number	1	2	3	4	5	6	7	8	9	For ED participants, follow the SFU procedures. Participants will complete either SFU or ED.
Study Days Relative to Randomization (Site Visits) or to Next Visit (Phone Calls)	-28 to -14	3 days before Visit 3	0	3 days before Visit 5	13 to 16	20 to 23 (day before first dose of crossover period)	3 days before Visit 8	34 to 37	SFU: 4 to 10 days after last dose (Visit 8) ED: ≥4 days after last dose	Study visits can fall within the day ranges listed here, but all assessments must occur on the same day. Phone contact columns (for Visits 2, 4, 6, 7) are in gray.
Site Visit	X		X		X			X	X	Visit 9 can be virtual or onsite based on local regulations and/or site preference.
Phone Contact		X		X		X	X		X	
Informed Consent	X									See Section 8.1.1 and Section 10.1.3
Review Inclusion/Exclusion Criteria	X		X							See Section 5
Demographics	X									
Height	X									See Section 8.4.1
Weight	X		X		X			X		BMI should be determined at Visits 1 and 3. Each calculation can use Screening height. See Section 8.4.1
Medical History	X		X							See Section 8.1.3
Adverse Events					X			X	X	See Section 8.5
Sleep Habits Assessment	X									See Section 8.3.1 [REDACTED]
Physical Examination	X									See Section 8.4.1
Caffeine and/or Nicotine Intake Assessment	X		X		X			X		Participants should be asked about their caffeine and/or nicotine intake the morning prior to arriving at study site See Section 5.3.1 and Section 8.3.4
Urine Drug Screen (dipstick)	X		X		X			X		See Section 8.4.6
Breath Alcohol Screen	X		X		X			X		See Section 8.4.6
Vital Signs	X		X		X			X		For BP, 3 readings are required. See Section 8.4.2
12-Lead ECG	X									See Section 8.4.3

Table 3: Schedule of Assessments (Continued)

Procedure	Screening		Baseline / Randomization	Double-blind Treatment Period (Treatment Period 1)		Washout Period	Double-blind Crossover Treatment Period (Treatment Period 2) (First Dose Taken Day 21 to 24)	SFU or ED	Notes	
Visit Number	1	2	3	4	5	6	7	8	9	

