8.1.7. Reminder Phone Calls

There will be several reminder phone calls made to participants throughout the study. If phone calls are not feasible, at their discretion sites can give participants the opportunity to “opt in” to an alternate, Health Insurance Portability and Accountability Act (HIPAA)-compliant method of contact; however, sites must record in source documents confirmation that notification was received.

The first phone contact is Visit 2, and should occur 3 days prior to Visit 3 (Baseline/Randomization). Participants will be reminded to:

- complete their sleep diary for 3 nights and bring the diary with them to site visit
- bring their PAP device
- not drink more than 200 mg of caffeine (eg, 2 cups of 8 oz coffee) the morning of the visit (see [Section 5.3.1](#) for details)
- get the usual night’s sleep the night before the site visit
- abstain from alcohol 24 hours before the site visit

The site will also confirm that the participant does not have plans to travel over the next 3 days and request the participant restrict any significant travel (eg, crossing time zone) before next visit.

The second phone contact is Visit 4, and should occur 3 days before Visit 5 (Treatment Period 1). Participants will be reminded to:

- complete their sleep diary for 3 nights and bring diary with them to site visit
- bring their PAP device
- bring all medications and medication bottles/blister packs
- not drink more than 200 mg of caffeine (eg, 2 cups of 8 oz coffee) the morning of the visit (see [Section 5.3.1](#) for details)

- get the usual night's sleep the night before the site visit
- abstain from alcohol 24 hours before the site visit
- not to take study drug on day of the visit

The site will also confirm that the participant does not have plans to travel over the next 3 days and request the participant restrict any significant travel (eg, crossing time zone) before next visit.

The third phone contact is Visit 6, and should occur during the Washout Period 1 day before the first dose of Treatment Period 2 intervention. Participants will be reminded to begin taking crossover treatment next morning, and to continue taking it until the next site visit.

The fourth phone contact is Visit 7, and should occur 3 days before Visit 8 (Treatment Period 2). This reminder call is identical to the reminder phone call Visit 4.

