## 11. SAFETY ANALYSES

Safety analyses will be performed on the Safety Population. Safety evaluations will be based on the incidence and severity of adverse events, as well as on ECG measurements, vital signs and Columbia Suicide Severity Rating Scale (C-SSRS). Safety variables will be tabulated and presented by study drug actually received.

In this crossover study, AEs will be attributed to the last treatment the participant received prior to the AEs.

Because there is no pre-specified safety outcome defined in terms of AEs or vital signs, any formal comparisons between the treatment arms with respect to specific safety parameters will be post-hoc.

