### For Adverse Events

If onset date is completely missing, onset date is set to date of first dose.

If (year is present and month and day are missing) or (year and day are present and month is missing):

- If year = year of first dose, then set month and day to month and day of first dose
- If year < year of first dose, then set month and day to December 31.
- If year > year of first dose, then set month and day to January 1.

If month and year are present and day is missing:

- If year = year of first dose and
  - If month = month of first dose then set day to day of first dose
  - If month < month of first dose then set day to last day of month
  - If month > month of first dose then set day to first day of month
- If year < year of first dose then set day to last day of month
- If year > year of first dose then set day to first day of month

For all other cases, set onset date to date of first dose.

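### Minor washout adverse events are first asked about at Visit 8, after crossover, although the call the day before crossover could ask about them and attribution depends on onset date

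*Protocol*

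**What the plan says.** Protocol Section 8.5.1 ties collection to the schedule: "All AEs and SAEs will be collected from the start of intervention until the follow-up visit at the time points specified in the SoA". In the SoA (Protocol Section 1.3, repeated as SAP Table 2) the adverse event row is marked at Visits 5, 8 and 9 and nowhere else.

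The SoA also lists four telephone contacts: "Phone contact columns (for Visits 2, 4, 6, 7) are in gray". Visit 2 precedes Baseline. Of the others, Visit 6 is timed against the switch of treatment. The SoA places it at Day "20 to 23 (day before first dose of crossover period"), and Protocol Section 8.1.7 says "The third phone contact is Visit 6, and should occur during the Washout Period 1 day before the first dose of Treatment Period 2" intervention. Its stated tasks are to confirm that no drug was taken for a week and to tell the participant to start the next morning. No adverse event question appears in the SoA cell or in the call content.

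SAP Section 11 sets the attribution rule: "AEs will be attributed to the last treatment the participant received prior to the AEs". SAP Section 11.2 defines treatment emergence by onset date, from first dosing to 7 days after last dosing.

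Protocol Appendix 4 supplies a second route. Participants are to contact the site as soon as possible about medically attended events and about other events that concern them. Events that are neither are gathered by interview at the next visit.

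**The concern.** In this crossover, the date of onset relative to the first Period 2 dose decides which treatment an event is counted against. A washout event belongs to the Period 1 treatment. If it is remembered as starting a few days later than it did, it moves to the other treatment.

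The plan asks for that date only after the participant has taken the whole second treatment, although the site speaks to the participant on the last drug-free day. At stake is the accuracy of the incidence and severity of treatment-emergent events by treatment, which the protocol lists under its safety objective.

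**Working it through.** **Inputs (SoA, Protocol Section 1.3)**
- Visit 5, last Period 1 dose: Day 13 to 16.
- Visit 6, washout call: Day 20 to 23.
- Period 2: "First Dose Taken Day 21 to 24".
- Visit 8, last Period 2 dose: Day 34 to 37.

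Nominal means that every visit falls at the same position in its window, for example Days 13, 20, 21 and 34.

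**Step 1: reproduce the plan's own intervals.**
- Drug-free days = first Period 2 dose − Visit 5 − 1 = 21 − 13 − 1 = 7 (also 24 − 16 − 1 = 7).
- Period 2 dosing days = Visit 8 − first dose + 1 = 34 − 21 + 1 = 14.

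Both match the stated 1-week washout and 2-week treatment period.

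**Step 2: gap between scheduled adverse event questions.**
- Nominal: 34 − 13 = 21 days (37 − 16 = 21).
- Shortest across windows: 34 − 16 = 18 days.
- Longest across windows: 37 − 13 = 24 days.

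**Step 3: delay from onset of a washout event to the first scheduled question, as planned.** Delay = Visit 8 − onset day.
- Nominal, onset on the first washout day (Day 14): 34 − 14 = 20 days.
- Nominal, onset on the last washout day (Day 20): 34 − 20 = 14 days.
- Across windows, shortest: 34 − 23 = 11 days.
- Across windows, longest: 37 − 14 = 23 days.

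For anyone who continues into Period 2, the question comes after crossover in every case. Protocol Section 8.3.2 lets visit windows be extended for poor sleep or travel, so 23 days is not a hard ceiling.

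**Step 4: the same delay with a question at Visit 6.** Delay = Visit 6 − onset day.
- Nominal: 20 − 20 = 0 to 20 − 14 = 6 days.
- Across windows, longest: 23 − 14 = 9 days.

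The question then always precedes crossover.

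**Step 5: direction of the error.** Let each sequence have *n* participants. Let *a* be the mean number of washout events per participant after solriamfetol and *b* the mean after placebo. Let *p* be the chance that such an event is dated after the first Period 2 dose, assumed equal in both sequences. The solriamfetol-minus-placebo difference in washout events is *n*(*a* − *b*) when dated correctly. With misdating it is *n*[*a*(1 − *p*) + *bp*] − *n*[*b*(1 − *p*) + *ap*] = *n*(*a* − *b*)(1 − 2*p*). If *a* = *b* nothing changes. Otherwise, for *p* below one half, the difference shrinks but keeps its sign. The documents give no value for *p*, *a* or *b*, so the number of affected events cannot be computed.

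**The case against.** The strongest defence is that the plan does provide a route before Visit 8. Appendix 4 asks for prompt contact about medically attended or concerning events, and serious events must reach the sponsor within 24 hours of site knowledge. This stands, and it confines the point to minor events.

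The washout also protects most Period 1 events. Nominally, an event during Period 1 dosing would have to be dated more than a week late to fall in Period 2. Sequences are assigned 1:1 and double-blind, and Protocol Section 9.4.5 plans no formal safety testing. These arguments also stand. They limit the harm to blurring of a descriptive summary.

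It can also be said that the calls have visit numbers, so interview at the next visit might include Visit 6. The blank SoA cell and the call content point the other way, as does Protocol Section 4.1.3, which schedules the visit after Visit 5 for the end of Period 2. Section 8.5.3 mentions contacts, but only for following up an event already reported.

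A reader might infer more than the documents support:
- *That all three on-study calls need the question, partly because of the step from 75 mg to 150 mg.* Visits 4 and 7 fall only 3 days before a site visit that already asks. In Period 1 the step comes on Day 4 and Visit 4 on Day 10 to 13, which is 6 to 9 days later. A question there would gain 3 days.
- *That date imputation makes the problem materially worse.* The SAP says "If onset date is completely missing, onset date is set to date of first dose", but that rule is for wholly missing dates, and most partial dates are handled by comparing the recorded month and year with those of first dose. Nothing indicates how often such dates will occur. Whether a Period 2 rule is needed is a separate SAP question that a telephone question does not settle.
- *That concomitant medications should be added to the call.* No stated problem in the documents calls for it.

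**Conclusion.** The point holds as a cheap improvement. The documents are consistent with one another here. The weakness is a missed opportunity to date minor washout events before treatment changes. For events that are neither medically attended nor of concern to the participant, the first scheduled question comes nominally 14 to 20 days after onset and after crossover. It could come 0 to 6 days after onset and before crossover.

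This rests on three assumptions: the SoA and call content are followed as written, the participant continues into Period 2 (those who stop early are asked at the early discontinuation visit), and recall of onset worsens with delay.

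A reader might infer directional bias in favour of solriamfetol, or that events have no route to the site for three weeks. Neither is supported. With blinded 1:1 sequences the misdating is most likely non-differential, and prompt self-report covers the events that matter most clinically. Primary and secondary efficacy analyses are unaffected.

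**What to change.** Mark adverse events in the SoA at phone Visit 6, in both the protocol and the SAP copy. Add one item to the Visit 6 call in Protocol Section 8.1.7: a single open-ended question, in the non-leading style that Section 8.5.2 already prefers, with the onset date recorded during the call. No change is needed at Visits 4 or 7.

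The cost is a few minutes on a call already made, slightly more minor events reported and a little more data entry. SAP Section 10.7 says the new sponsor has decided to conclude the study, so the change can help only for Visit 6 calls not yet made.

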8.5.2. Method of Detecting Adverse Events and Serious Adverse Events

Care will be taken not to introduce bias when detecting AEs and/or SAEs. Open-ended and nonleading verbal questioning of the participant is the preferred method to inquire about AE occurrences.

8.5.3. Follow-up of Adverse Events and Serious Adverse Events

After the initial AE/SAE report, the investigator is required to proactively follow each participant at subsequent visits/contacts. All SAEs will be followed until resolution, stabilization, the event is

otherwise explained, or the participant is lost to follow-up (as defined in [Section 7.3](#)). Further information on follow-up procedures is provided in [Appendix 4](#).

8.5.4. Regulatory Reporting Requirements for Serious Adverse Events

- Prompt notification by the investigator to the sponsor of an SAE is essential so that legal obligations and ethical responsibilities towards the safety of participants and the safety of a study intervention under clinical investigation are met.
- The sponsor has a legal responsibility to notify both the local regulatory authority and other regulatory agencies about the safety of a study intervention under clinical investigation. The sponsor will comply with country-specific regulatory requirements relating to safety reporting to the regulatory authority, Institutional Review Boards (IRB)/Independent Ethics Committees (IEC), and investigators.
- An investigator who receives an investigator safety report describing an SAE or other specific safety information (eg, summary or listing of SAEs) from the sponsor will review and then file it along with the IB and will notify the IRB/IEC, if appropriate according to local requirements.
- Investigator safety reports will be prepared for suspected unexpected serious adverse reactions (SUSARs) according to local regulatory requirements and sponsor policy and forwarded to investigators as necessary. The Reference Safety Information for the determination of expectedness of solriamfetol can be found in the IB.

8.5.5. Pregnancy

- Details of all pregnancies in female participants and female partners of male participants will be collected after the start of study intervention and until 14 days after the last dose of the study intervention.
- If a pregnancy is reported, the investigator will record pregnancy information on the appropriate form and submit it to the sponsor within 24 hours of learning of the female participant or female partner of male participant (after obtaining the necessary signed informed consent from the female partner) pregnancy.
- While pregnancy itself is not considered to be an AE or SAE, any pregnancy complication or elective termination of a pregnancy for medical reasons will be reported as an AE or SAE.
- Abnormal pregnancy outcomes (eg, spontaneous abortion, fetal death, stillbirth, congenital anomalies, ectopic pregnancy) are considered SAEs and will be reported as such.
- The participant (or the participant's pregnant female partner) will be followed to determine the outcome of the pregnancy. The investigator will collect follow-up information on the participant (or the participant's pregnant female partner) and the neonate, and the information will be forwarded to the sponsor.
- Any post-study pregnancy-related SAE considered reasonably related to the study intervention by the investigator will be reported to the sponsor as described in [Section 8.5.4](#). While the investigator is not obligated to actively seek this information

in former study participants (or the participant's pregnant female partner), he or she may learn of an SAE through spontaneous reporting.

- Any female participant who becomes pregnant while participating in the study will discontinue study intervention or be withdrawn from the study.

8.5.6. Overdose, Medication Errors, and Misuse

Overdose (defined as any dose administered or received that was higher than the intended dose), medication errors (defined as any unintentional error in the dispensing or administration of the study drug), and misuse of the study drug are considered reportable experiences. The method for completing and transmitting reports of these experiences are provided in [Appendix 4](#).

If any overdose, medication error, or misuse of the study drug results in an AE, this must be recorded. If the AE is serious, it must also be reported as described in [Appendix 4](#).

Decisions regarding dose interruptions or modifications will be made by the investigator in consultation with the Medical Monitor based on the clinical evaluation of the participant.

8.6. Pharmacokinetics

Pharmacokinetics will not be evaluated in this study.

8.7. Genetics

Genetics will not be evaluated in this study.

8.8. Biomarkers

Biomarkers will not be evaluated in this study.

8.9. Immunogenicity Assessments

Immunogenicity assessments are not applicable to this study.

8.10. Health Economics

Health economics will not be evaluated in this study.

9. STATISTICAL CONSIDERATIONS

9.1. Statistical Hypotheses

9.1.1. Primary Hypothesis

The primary statistical hypothesis for this study is to show whether solriamfetol has a significantly improved effect versus placebo on the primary endpoint of the changes in average DSST scores (average of the postdose DSST scores [hour 2, 4, 6, and 8] versus average of the Baseline DSST scores) after 2 weeks of treatment ($H_1: \mu_{sol} - \mu_{pl} > 0$) using a 1-sided significance level of 0.025. The statistical null hypothesis is that solriamfetol does not improve versus placebo on the change in DSST scores after 2 weeks of treatment ($H_0: \mu_{sol} - \mu_{pl} \leq 0$).

9.2. Sample Size Determination

A sample size of 49 participants per treatment sequence for a total sample size of 98 will provide 90% power to detect a difference of 3 points in means for the change from Baseline to Week 2 on DSST RBANS scores between solriamfetol and placebo, assuming a standard deviation of 9 points in the change in DSST (the cross over analysis of variance [ANOVA] root mean squared error (RMSE) is 6.36). The sample size estimates are based on the results from Trintellix randomized parallel placebo-controlled trials ([McIntyre 2014](#); [Mahableshwarkar 2015](#)). The change from Baseline to Week 8 resulted in an estimated delta on DSST performance score of 1.8 ~ 4.3 (average 3.4) and SD of 6.6 ~ 8.6. Another reference is a crossover study with 5 dosages of MK-0249, modafinil 200 mg, and placebo and each period is 2 weeks, the RMSEs are estimated from 4.4 ~ 5.7 ([Herring 2013](#)). It is increased to 6.36 to account for uncertainty in sample size assumptions. A 1-sided significance level of 0.025 using a 2 group t-test (crossover ANOVA) is used in the sample size calculation. Assuming a correlation of 0.5 between periods on DSST, a delta of 3, a standard deviation of 9, and a 15% dropout rate, a total of 116 (58 participants per treatment sequence) will be randomized.

Note: “Randomized” means a participant who consented to the study and was assigned to a randomized treatment group and received at least 1 dose of study intervention.

9.3. Analysis Populations

Population	Description
Safety	All randomized participants who receive at least 1 dose of study intervention. This analysis set will be used for safety analyses and participants should be summarized according to actual treatment. This population will be analyzed for safety evaluations and will be presented in the tables and listings of safety data.
ITT	All randomized participants.
mITT	All participants who were randomized, received at least 1 dose of study medication, have Baseline and at least 1 postdose evaluation of DSST. If a participant in the mITT population does not have an assessment for a particular endpoint, it will be excluded in the analysis of that endpoint. The primary efficacy analyses will be based on the mITT population.

Abbreviations: DSST = Digit Symbol Substitution Test; ITT = Intent-to-Treat; mITT = modified ITT

